7.1. Visit Windows and Relative Days

The complete list of visit windows used throughout the study is provided in [Appendix 1](#).

For efficacy summary tabulations, the visit windows will be used as they apply to the evaluation schedule for each endpoint. In the case of multiple visits per reporting window, the visit closest to the midpoint of the interval will be used for summary assessments. If there are multiple visits equally distant from the midpoint of a window, then the earlier visit will be used. These windows apply to, tumor response, bone scans, site assessment of disease, and Karnofsky performance status tumor markers.

For safety tabulations, day of measurement is computed relative to date of each dose until the next dose occurs, for example prior to the first therapeutic infusion until the second therapeutic infusion occurs, then relative to the second therapeutic infusion. These windows apply to ECGs, vital signs and labs. The visit windows for each assessment (vital signs, ECGs, laboratory tests) are specified in [Appendix 1](#) as the scheduled evaluations vary by assessment.

ECGs will be obtained and summarized for readings within 15 minutes prior to the second and third imaging scans as well as those obtained within seven days following each therapeutic dose.

Vital signs will be summarized for readings 4 hours prior and 4 hours post each dose.

Laboratory results taken within 24 hours post imaging and first therapeutic dose and 48 hours post second therapeutic dose will be summarized in addition to those visits where the assessment are scheduled.

Relative days:

The following relative days will be computed for subjects:

For all subjects and visit dates, compute SDAY (Study day) as assessment date minus informed consent date + 1.

For subjects with at least one dose and visit dates:

- TDAYDOS1 (Treatment day from 1st dosimetry) as assessment date minus date of first dosimetry dose + 1.
- TDAYDOS2 (Treatment day from 2nd dosimetry) as assessment date minus date of second dosimetry dose + 1 for any subjects who received a second dosimetry dose.
- TDAYTX1 (Treatment day from therapeutic dose 1) as assessment date minus date of first therapeutic dose + 1; missing for subjects with only a dosimetry dose.
- TDAYTX2 (Treatment day from therapeutic dose 2) as assessment date minus date of second therapeutic dose + 1; missing for subjects with only 1 therapeutic dose and also for subjects with only a dosimetry dose.

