Use of antihypertensive medication will be measured through standard, ongoing reporting of concomitant medications throughout the study until completion of the follow-up period. Tumors will be measured by computed tomography (CT) with contrast or magnetic resonance (MR) imaging at baseline and at 3, 6, 9 and 12 months after the first Therapeutic Dose. Obtaining renal volume for each kidney is required at baseline. A bone scan will be performed at Screening/baseline and if probable metastatic disease is observed or suspected, additional bone scans will be performed at Month 3, 6, 9, 12. Overall tumor response at 3, 6, 9 and 12 months per RECIST criteria will be assessed centrally by independent, blinded readers. FDG scans may also be performed at baseline and 3, 6, 9, and 12 months to assess viable tumor tissue. Tumor markers [serum chromogranin A, plasma free metanephrines and normetanephrines, 24 hour urinary vanillylmandelic acid (VMA), plasma catecholamines (dopamine, epinephrine and norepinephrine), 24 hour urinary catecholamines (dopamine, epinephrine and norepinephrine) and urinary metanephrines and normetanephrines] will be evaluated by a central laboratory. Testing for tumor markers will occur at baseline, every two weeks for the first 24 weeks after the first Therapeutic Dose starting at Week 2, and monthly during months 7-12. Renal function will be assessed through either creatinine clearance or Glomerular Filtration Rate (GFR) at baseline and at the Months 6 and 12 Efficacy Visits. Evaluation of thyroid function (T3, T4 and TSH) and clinical evaluation of possible dry mouth will be performed at the 12 month Efficacy Visit. Use and dose of antihypertensive, pain and other medication required for tumor associated signs and symptoms will be recorded on an on-going basis throughout the study until completion of the follow-up period. Subject-reported Quality of Life measurements will be obtained through the EORTC QLQ-C30 v3 and the NIH Quality of Life and Symptoms Questionnaire for Pheochromocytoma and Paraganglioma. The frequency of the procedures is summarized in the Schedule of Procedures (Appendix VII). Subject may undergo additional assessments as warranted (for example, to confirm tumor response) at unscheduled visits.

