9.3 Study Duration

Subjects will attend study visits from the time of signed informed consent through 12 months (efficacy portion) and a 5 year follow-up period after the first Therapeutic Dose of Ultratrace iobenguane I 131. Subjects will be monitored for AE/SAE and Adverse Events of Special Interest (including post radiation toxicity) as described in Section 12. Subjects may undergo additional assessments to confirm response, or as part of institutional standard of care during long-term follow-up. Figure 1 outlines the study period; a more extensive summary of study procedures is given in the Schedule of Procedures (Appendix VII).

FIGURE 1: STUDY DURATION

Signed informed consent, subject enters study Eligibility/dosimetry study Imaging Dose (3 to 6 mCi) of Ultratrace iobenguane I 131 administered within 30 days of first therapeutic dose followed by three I 131 whole body scans to confirm uptake and to determine dosimetry First Therapeutic Dose of Ultratrace iobenguane I 131 administered day 0 I 131 scan within seven days post first therapeutic infusion to assess biodistribution Safety visit 6 weeks post-first Therapeutic Dose Objective tumor response assessments 3 months post-Therapeutic Dose and prior to the second Therapeutic Dose Second Therapeutic Dose Ultratrace iobenguane I 131 administered starting at month 3, at least 12 weeks after the first Therapeutic Dose. I 131 scan within seven days after second Therapeutic Dose Safety visit 6 weeks post second Therapeutic Dose Tumor response assessments, tumor markers (every two weeks through week 24 and monthly from month 7-12), physical exam at months 3 (prior to the second Therapeutic Dose, if administered), 6, 9 and 12 Subject completes regularly scheduled study visits at month 12 Long-term follow-up for adverse events of special interest, overall survival, tumor markers and disease status (inc. clinical benefit) through year 5

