Concomitant Medications			Concomitant	Concomitant medications taken throughout the study will be recorded	throughout the stu	dy will be recor	ded		
Hematology, Chem, UA ⁵	Х	Х	Х		Week 2-Week 24	Х	1x month (Months 7-12)		
TSH, T3, T4	Х							X (Month 12 ONLY)	

MIP-IB12B_CSP_V1a3_21Mar2014 CONFIDENTIAL

Ultratrace Iobenguane I 131 Protocol No. MIP-IB12B	31	APPENDIX	VII: SCHED	DIX VII: SCHEDULE OF PROCEDURES	DCEDURES			Pheochro Page 97	Pheochromocytoma Page 97
	Screening/ Baseline	Imaging Dose/ Scans	Therapeutic Doses	Ultratrace I 131 Scan	Post Therapy I	Post Each Therapy	Post Therapy I	y I	Long Term Follow Up* Every 6 mo
Procedure/Test	Week -4 to Imaging Dose	Imaging Dose within 30 days of therapeutic dose	Day 0 and Month 3*	Within 7 days after each therapeutic dose	Weekly through 24 Weeks	6 weeks after each therapy	Monthly post 1 st Therapy	3, 6, 9 ,12 Months post 1st Therapy	Years 2 through 5 after 1st Therapy
Renal function (GFR or 24 hr $CC)^6$	Х							Month 6 & 12	
Renal Volume	Х								
Tumor Markers	X				Every 2 weeks during weeks 2-24		1x month (Months 7-12)		X
Pregnancy Test, serum or urine(if applicable)	X (serum)	X (urine, within 48hrs prior to dose)	X (urine, within 48 prior to dose)						
CT or MR Scan of chest, pelvis and abdomen ^{7}	Х							X	Х
Optional FDG scan	Х							Х	
Bone Scan ⁸	X							X^8	
ECG ⁹		Х		Х					
Holter Monitor (24 hours) ¹⁰			Х						
SSKI Administration ¹¹		X (Day -2 to Day 0)	Х						
Imaging Dose 3 to 6 mCi Ultratrace I 131		Х							
Imaging Scans Ultratrace I 131 ¹² (scintigraphic)		X (3)		Х					
Dosimetry Calculation for Therapy Dose		X (Day -2 to Day 0)							
Therapeutic Dose Ultratrace I 131			X(dose 1 on day 0 and dose 2 on Month 3)						
EORTC QLQ-C30 ^{13/} NIH Pheo Clinical Questionnaire ¹³	X (2)				Week 3,6,10,12,15, 18,22		Monthly Months 6- 12		

MIP-IB12B_CSP_V1a3_21Mar2014 CONFIDENTIAL

MIP-IB12B_CSP_V1a3_21Mar2014 CONFIDENTIAL

I 131	2B
enguane]	MIP-IB12B
obeng	, ,
	l No.
tratrace]	rotocol
Π	Ě

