APPENDIX 1. VISIT WINDOWS

These windows are intended for data summaries by time point. When multiple assessments fall within a window, the assessment closest to the nominal time will be used in summaries. If there are multiple visits equally distant from the midpoint of a window, then the earlier visit will be used.

Efficacy Assessments

No	End Point	From Imaging Dose 1	From Therapeutic Dose 1	From Therapeutic Dose 2
1	Overall Tumor Response (CT/MRI Scans)	Screening / Baseline (Day -28 to Day 0)	Month 3 (Day 81 - Day 101) Month 6 (Day 173 - Day 193) Month 9 (Day 264 - Day 284) Month 12 (Day 355 - Day 375) Month 18 (Day 518 - Day 578) Month 24 (Day 700 - Day 760) Month 30 (Day 883 - Day 943) Month 36 (Day 1065 - Day 1125) Month 42 (Day 1248 - Day 1308) Month 48 (Day 1430 - Day 1490) Month 54 (Day 1613 - Day 1673) Month 60 (Day 1795 - Day 1855)	
2	Tumor Markers	Screening / Baseline (Day -28 to Day 0)	Week 2 (Day 8 - Day 14) Week 4 (Day 22 - Day 28) Week 6 (Day 36 - Day 42) Week 8 (Day 50 - Day 56) Week 10 (Day 64 - Day 70) Week 12 (Day 78 - Day 84) Week 14 (Day 92 - Day 98) Week 16 (Day 106 - Day 112) Week 18 (Day 120 - Day 126) Week 20 (Day 134 - Day 140) Week 22 (Day 148 - Day 154) Week 24 (Day 162 - Day 168) Month 7 (Day 203 - Day 223)	

No	End Point	From Imaging Dose 1	From Therapeutic Dose 1	From Therapeutic Dose 2
			Month 8 (Day 233 - Day 253) Month 9 (Day 264 - Day 284) Month 10 (Day 294 - Day 314) Month 11 (Day 325 - Day 345) Month 12 (Day 355 - Day 375) Month 18 (Day 518 - Day 578) Month 24 (Day 700 - Day 760) Month 30 (Day 883 - Day 943) Month 36 (Day 1065 - Day 1125) Month 42 (Day 1248 - Day 1308) Month 48 (Day 1430 - Day 1490) Month 54 (Day 1613 - Day 1673) Month 60 (Day 1795 - Day 1855)	
3	Soloway Score (Bone Scan) and optional FDG-PET Scan	Screening / Baseline (Day -28 to Day 0)	Month 3 (Day 81 - Day 101) Month 6 (Day 173 - Day 193) Month 9 (Day 264 - Day 284) Month 12 (Day 355 - Day 375)	
4	Karnofsky Performance	Screening / Baseline (Day -28 to Day 0)	Day 1 Week 6 ± 10 days (Day 32 - Day 52) Month 3 (Day 81 - Day 101) Month 6 (Day 173 - Day 193) Month 9 (Day 264 - Day 284) Month 12 (Day 355 - Day 375)	Day 1 Week 6 ± 10 days (Day 32 - Day 52)

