5	Symptom Response (NIH Pheochromocytoma Clinical Questionnaire) and EORTC QLQ-30 Questionnaire	Screening / Baseline (Day -28 to Day 0) Note: two assessments are to be performed prior to the first therapeutic dose within this window	Week 3 (Day 15 - Day 21) Week 6 (Day 36 - Day 42) Week 10 (Day 64 - Day 70) Week 12 (Day 78 - Day 84) Week 15 (Day 99 - Day 105) Week 18 (Day 120 - Day 126) Week 22 (Day 148 - Day 154) Month 6 (Day 173 - Day 193) Month 7 (Day 203 - Day 223) Month 8 (Day 233 - Day 253)	

No	End Point	From Imaging Dose 1	From Therapeutic Dose 1	From Therapeutic Dose 2
			Month 9 (Day 264 - Day 284) Month 10 (Day 294 - Day 314) Month 11 (Day 325 - Day 345) Month 12 (Day 355 - Day 375)	
6	Tumor Pain Medication		Month 3 (Day 81 - Day 101) Month 6 (Day 173 - Day 193) Month 9 (Day 264 - Day 284) Month 12 (Day 355 - Day 375)	

Safety Assessments

No	End Point	From Imaging Dose 1	From Therapeutic Dose 1	From Therapeutic Dose 2
1	Vital Signs (pulse, temperature, respiration)	Screening / Baseline (Day -28 to Day 0) Day 1: 4 hours prior Day 1: 4 hours post	Day 1: 4 hours prior Day 1: 4 hours post	Day 1: 4 hours prior Day 1: 4 hours post
2	Vital Signs (body weight)	Day 1: prior to dosing	Day 1: prior to dosing	Day 1: prior to dosing
3	Vital Signs (BP and heart rate by Health Staff and Subject Readings)	Screening / Baseline (Day -28 to Day 0) Day 1: 4 hours prior Day 1: 4 hours post	Day 1: 4 hours prior Day 1: 4 hours post Week 1 (Day 2 - Day 7) 2x week Week 2 (Day 8 - Day 14) 2x week Week 3 (Day 15 - Day 21) 2x week Week 4 (Day 22 - Day 28) 2x week Week 5 (Day 29 - Day 35) 2x week Week 6 (Day 36 - Day 42) 2x week Week 7 (Day 43 - Day 49) Week 8 (Day 50 - Day 56) Week 9 (Day 57 - Day 63) Week 10 (Day 64 - Day 70) Week 11 (Day 71 - Day 77)	Day 1: 4 hours prior Day 1: 4 hours post Week 1 (Day 2 - Day 7) 2x week Week 2 (Day 8 - Day 14) 2x week Week 3 (Day 15 - Day 21) 2x week Week 4 (Day 22 - Day 28) 2x week Week 5 (Day 29 - Day 35) 2x week Week 6 (Day 36 - Day 42) 2x week Week 7 (Day 43 - Day 49) Week 8 (Day 50 - Day 56) Week 9 (Day 57 - Day 63) Week 10 (Day 64 - Day 70) Week 11 (Day 71 - Day 77)

No	End Point	From Imaging Dose 1	From Therapeutic Dose 1	From Therapeutic Dose 2

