			Week 12 (Day 78 - Day 84) Week 13 (Day 85 - Day 91) Week 14 (Day 92 - Day 98) Week 15 (Day 99 - Day 105) Week 16 (Day 106 - Day 112) Week 17 (Day 113 - Day 119) Week 18 (Day 120 - Day 126) Week 19 (Day 127 - Day 133) Week 20 (Day 134 - Day 140) Week 21 (Day 141 - Day 147) Week 22 (Day 148 - Day 154) Week 23 (Day 155 - Day 161) Week 24 (Day 162 - Day 168) Month 7 (Day 203 - Day 223) Month 8 (Day 233 - Day 253) Month 9 (Day 264 - Day 284) Month 10 (Day 294 - Day 314) Month 11 (Day 325 - Day 345) Month 12 (Day 355 - Day 375)	Week 12 (Day 78 - Day 84) Week 13 (Day 85 - Day 91) Week 14 (Day 92 - Day 98) Week 15 (Day 99 - Day 105) Week 16 (Day 106 - Day 112) Week 17 (Day 113 - Day 119) Week 18 (Day 120 - Day 126) Week 19 (Day 127 - Day 133) Week 20 (Day 134 - Day 140) Week 21 (Day 141 - Day 147) Week 22 (Day 148 - Day 154) Week 23 (Day 155 - Day 161) Week 24 (Day 162 - Day 168)
4	ECG and 24-Hour Holter Monitoring	Day 1: 2 hours prior (triplicate ECG) up to 2 minutes post 10 ± 2 minutes post 15 ± 2 minutes post 20 ± 2 minutes post within 15 minutes prior to imaging scans 2 and 3	Day 1 (24-hr Holter monitoring to begin between 100 to 45 minutes prior to dosing and to continue for approximately 23 hours following dosing) Week 1 (Day 2 - Day 8)	Day 1 (24-hr Holter monitoring to begin between 100 to 45 minutes prior to dosing and to continue for approximately 23 hours following dosing) Week 1 (Day 2 - Day 8)
5	Hematology, Chemistry & Urine Analysis	Screening / Baseline (Day -28 to Day 0) Day 1 within 24 hr prior	Day 1 within 24 hr prior Week 2 (Day 8 - Day 14) Week 3 (Day 15 - Day 21)	Day 1 within 48 hr prior Week 2 (Day 8 - Day 14) Week 3 (Day 15 - Day 21)

No	End Point	From Imaging Dose 1	From Therapeutic Dose 1	From Therapeutic Dose 2

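### The SAP counts the dosing day as Day 1 but keeps visit windows numbered from Day 0, so a sample on the last allowed day of a protocol window falls one day outside its SAP window

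*SAP*

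**What the plan says.** **Protocol.** Figure 1 in section 9.3 has "First Therapeutic Dose of Ultratrace iobenguane I 131 administered day 0", and the schedule of procedures in Appendix VII agrees: "dose 1 on day 0 and dose 2 on Month 3". In the window tables of section 11.5.18, Week 1 runs from Day 0 to Day 7, Week 2 from Day 8 to Day 14, and so on to Week 24 at Day 162 to 168. Monthly windows are ±10 days. Section 9.1 schedules tumor markers "every two weeks for the first 24 weeks after the first Therapeutic Dose starting at Week 2".

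**SAP.** Section 7.1 defines "TDAYTX1 (Treatment day from therapeutic dose 1) as assessment date minus date of first therapeutic dose + 1", and TDAYTX2 in the same way from the second dose. Appendix 1 has a column counted from Therapeutic Dose 1 and labels the dosing day Day 1. Its tumor-marker row nevertheless reads "Week 2 (Day 8 - Day 14) Week 4 (Day 22 - Day 28) Week 6 (Day 36 - Day 42", continuing for even weeks to Week 24 and then monthly. Its questionnaire row starts "Week 3 (Day 15 - Day 21) Week 6 (Day 36 - Day 42) Week 10 (Day 64 - Day 70". These are the protocol's day numbers. The ECG row has "Week 1 (Day 2 - Day 8".

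Section 7.4.7 tabulates confirmed tumor-marker response by visit window and correlates marker response at the 3, 6, 9 and 12 month windows. Section 7.4.8 summarizes quality of life by visit. Neither section 7.1 nor Appendix 1 says what happens to a value that falls in no window.

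**The concern.** The same number means a different date in the two documents. Protocol Day 14 is 14 days after the dose; SAP Day 14 is 13 days after it. If the limits are copied and the day count is not, each window moves one day earlier in calendar time. A compliant value at the late edge then leaves its window, and a value taken one day before the protocol window opens enters it.

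The affected day is not an unusual one. It is the exact-week day, when a subject returns on the weekday of dosing. The marker and questionnaire rows have gaps between windows, so such a value has no neighboring window to fall into and leaves the by-visit table without any flag. At stake are the completeness of secondary-endpoint summaries by visit, the window-based marker correlations, and the week labels of some blood-pressure and laboratory values.

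**Working it through.** **Step 1: which convention do the Appendix 1 windows follow?** Two entries can be rebuilt from their own descriptions.

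- Karnofsky, Week 6 ± 10 days, stated as Day 32-52. With dosing on Day 0: 6 × 7 = 42, and 42 ± 10 = 32 to 52, which matches. With dosing on Day 1: 43 ± 10 = 33 to 53, which does not.
- ECG within 7 days after each therapeutic dose (protocol 11.5.15), stated as Day 2-8. With dosing on Day 1: 1 + 1 = 2 to 7 + 1 = 8, which matches. With dosing on Day 0: 1 to 7, which does not.

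Appendix 1 therefore mixes both conventions. The Karnofsky cell does so by itself, because it also lists the dosing day as Day 1.

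**Step 2: tumor markers.** For week w, the protocol window is 7w − 6 to 7w days after the dose. The SAP uses the same limits, but TDAYTX1 = days after dose + 1. The last allowed day, 7w, becomes 7w + 1. The next marker window opens at 7(w + 2) − 6 = 7w + 8, so Days 7w + 1 to 7w + 7 belong to no window.

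- Days after dose: 14, 28, 42, 56, 70, 84, 98, 112, 126, 140, 154, 168.
- TDAYTX1: 15, 29, 43, 57, 71, 85, 99, 113, 127, 141, 155, 169.
- In a marker window: 0 of 12. (After Week 24 the next window, Month 7, opens at Day 203.)

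**Step 3: questionnaires** (Weeks 3, 6, 10, 12, 15, 18, 22).

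- Days after dose: 21, 42, 70, 84, 105, 126, 154.
- TDAYTX1: 22, 43, 71, 85, 106, 127, 155.
- In a questionnaire window: 0 of 7.

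**Step 4: contiguous weekly rows.** In the laboratory row after dose 1 (Weeks 2 to 24, 23 windows), 22 exact-week values take the next week's label, and the Week 24 value (Day 169) falls in no window. The weekly blood-pressure row behaves in the same way. Values on the other six days of each of these weeks keep their label.

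**Step 5: monthly windows.** At the nominal day nothing is lost: Month 7 has midpoint 213, which becomes 214, inside 203-223. That gives 0 of 6 marker visits and 0 of 7 questionnaire visits lost. Only the last allowed day moves out (for example 223 becomes 224).

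**Step 6: share of allowed days affected.**

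| | Week windows | Monthly windows |
|---|---|---|
| Tumor markers | 12 of 84 (1 in 7) | 6 of 126 (1 in 21) |
| Questionnaires | 7 of 49 (1 in 7) | 7 of 147 (1 in 21) |

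If visits were spread evenly over the allowed days (an assumption), about 14% of week-window values and 5% of monthly-window values would be lost. For one subject's biweekly marker samples the range is 0 of 12 (never seen on the last day) to 12 of 12 (always seen on it).

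**Step 7: after the change.** With both limits raised by 1, every allowed day d in a protocol window a to b becomes d + 1 in a + 1 to b + 1. All 18 marker visits and all 14 questionnaire visits through Month 12 then fall in their own window at the nominal day.

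**The case against.** Four points can fairly be made on the other side.

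- **No nominal Day 14 exists.** Protocol 11.5.18 asks for a visit between two days, and any of the seven is on schedule. This stands. A reader might infer that on-schedule samples are lost in general, but the documents support only the loss of the last allowed day. The counts of 12 of 12 and 7 of 7 describe one constructed attendance pattern.
- **TDAYTX1 is not named as the windowing variable.** SAP 7.1 lists it among the days to be computed and does not state the link. This stands as a limit on certainty. Still, it is defined in the section on visit windows, it is the only day variable defined from the first therapeutic dose, and Appendix 1 labels that dosing day Day 1. If a count without the +1 was intended, the Day 1 labels and the ECG window are the entries that are wrong, so the inconsistency remains.
- **The consequence is small.** The windows serve summaries by time point. All marker measurements are listed, and confirmation rests on the subsequent assessment rather than on a window. This stands.
- **Questionnaires are a weaker case.** The sentence in 7.1 that lists windowed efficacy assessments omits them. Appendix 1 nevertheless gives them windows, and no other visit assignment is described.

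A reader might also infer that weekly blood-pressure and laboratory values are all labeled a week late. Step 4 shows that only the exact-week value moves.

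**Conclusion.** The mismatch is real and shows within Appendix 1 itself. Followed as written, with TDAYTX1 assigning windows, the SAP leaves compliant marker and questionnaire values on the last allowed day out of the by-visit tables and relabels the corresponding weekly blood-pressure and laboratory values. The documents give no visit dates, so the number of values affected cannot be computed.

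The effect is confined to by-visit summaries, the blood-pressure means by visit window in the figures, and the window-based correlations at Months 3 to 12. It might be inferred that the trial's main result is exposed. It is not: SAP 7.4.1 and 7.4.2 derive the primary endpoint from medication and disposition dates, not from these windows. Best confirmed marker response and overall marker responder status are not stated to be limited to windowed values either. The correction is worth making because it is cheap and the omission would otherwise go unnoticed.

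**What to change.** 1. State in SAP 7.1 that TDAYTX1 and TDAYTX2 assign the post-dose windows.
2. In Appendix 1, add 1 to both limits of the post-dose week and month windows: for example Week 2 = Day 9-15, Week 24 = Day 163-169, Karnofsky Week 6 = Day 33-53 (after each dose), Month 3 = Day 82-102.
3. Treat blood-pressure Week 1 separately. It is now Day 2-7. Shifting both limits would leave Day 2 without a window, and leaving it alone would leave Day 8 without one once Week 2 starts at Day 9. Set it to Day 2-8.
4. Leave the Screening, Day 1 and ECG Day 2-8 entries as they are.

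The alternative is to assign windows by assessment date minus dose date without the +1. The Day 1, blood-pressure Week 1 and ECG entries must then be changed to match.

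The cost is an edit to one SAP section and its appendix and a small programming change. No new data are needed.

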7.2. Subject Disposition and Characteristics

7.2.1. Subject Disposition

The summary of disposition of subjects includes the number and percentage of subjects in each analysis population, subjects who completed the efficacy phase, completed long-term follow-up, and subjects discontinued from study, as well as the reason for study discontinuation and the last follow-up status (Alive, Dead). The Enrolled Set will be used for this summary (this is the only table based on the full Enrolled Set). The disposition data will be listed as well, including reasons for those subjects who did not receive a therapeutic dose of study medication.

